9.2 Study Visit Procedures

9.2.1 Day -42 (Screening) Procedures

Subjects will report to clinic fasted. The Screening procedures should be all be completed within 42 days from consent in order to randomize the subject.

- Obtain informed consent
- Collect demographic data
- Ascertain medical history
- Collect smoking history
- Assess inclusion/exclusion criteria
- Measure height
- Measure body weight, BMI, waist circumference
- [REDACTED]
- [REDACTED]
- Complete AUDIT-C alcohol consumption questionnaire
- Obtain 12-lead ECG (after subject has been supine for at least 5 minutes)
- Measure vital signs (including temperature, respiratory rate, and seated blood pressure and pulse)
- Register screened subject [REDACTED]
- Record prior and concomitant medications
- Record AEs (starting from the when the subject signs informed consent)
- Obtain blood for 10-hour fasted laboratory sample collection for:
 - Chemistry
 - CBC
 - HbA1c
 - Insulin level
 - HOMA-IR calculation
 - INR
 - Alfa fetoprotein (AFP)
 - Serum pregnancy test (all female subjects of childbearing potential)
 - Hepatitis and HIV screen
 - PEth alcohol screen
 - Lipid panel
- Obtain urine for 10-hour fasted laboratory sample collection for:
 - Urinalysis
 - Urine drug screen

- Subjects with a local historical biopsy will have their slides evaluated and read by the central pathologists to ensure eligibility prior to undergoing MRI-PDFF

9.2.2 Day -28 to Day -1 (Screening) Procedures

Subjects will report to clinic fasted. Day -28 Screening procedures must be completed no sooner than 14 days (2 weeks) +3 days after the Day -42 Screening visit to allow for adequate separation of liver function tests.

- Obtain blood for 10-hour fasted laboratory sample collection for:
 - Chemistry
- Obtain urine for 10-hour fasted laboratory sample collection for:
 - Pre-dose serum pregnancy in all females of childbearing potential
- Obtain an MRI-PDFF assessment (preferably prior to any histologic evaluation unless a historical biopsy is available)
- Obtain viable tissue slides from eligible historical liver biopsy or undergo a liver biopsy procedure to obtain new tissue
- Record concomitant medications
- Record AEs

9.2.3 Day 1 Procedures

Subjects will report to clinic fasted. The following procedures will be performed at the Day 1 Visit:

Pre-dose:

- Reassess inclusion/exclusion criteria
- Measure body weight, BMI, and waist circumference
- [REDACTED]
- Obtain 12-lead ECG (after subject has been supine for at least 5 minutes)
- Measure vital signs (including temperature, respiratory rate, and seated blood pressure and pulse)
- Randomize subject [REDACTED] for aldafermin/matched placebo study-drug kit assignment
- Record concomitant medications
- Record new and/or changes to AEs
- Obtain 10-hour fasted clinical laboratory samples for the following:
 - Chemistry

- CBC
 - HbA1c
 - Insulin level
 - HOMA-IR calculation
 - [REDACTED]
 - INR
 - Lipid panel
 - Lipoprotein particles
 - Lipase
 - C4 and serum bile acids
 - PK (pre-dose)
 - Anti-drug antibodies (ADAs)
 - Neutralizing antibodies (NAbS)
 - ELF panel
 - Pro-C3
- [REDACTED]
- [REDACTED]
- [REDACTED]
- Blood sample (pre-dose) for genetic biomarker testing
 - pre-dose serum pregnancy in all females of childbearing potential
- Obtain urine for 10-hour fasted laboratory sample collection for:
 - urinalysis
 - urine drug screen

In-clinic dosing and assessments:

- Dispense initial aldafermin/matched placebo study-drug kit and home diary
- Provide aldafermin/matched placebo study-drug self-administration training.
- Oversee subject's aldafermin/matched placebo study-drug self-administration.
- Perform local injection-site symptom assessment (LISSA) evaluation.

Before clinic discharge:

- Obtain 2-hour post-dose PK sample

- Remind subject to bring study-drug kit/diary and to not self-inject aldafermin/matched placebo on clinic visit days
- Schedule Week 2 visit

For Optional PK Sub-study Subjects:

For those subjects participating in the optional PK sub-study, PK samples will be collected before subjects dose themselves in the clinic and post-dose at 0.5, 1, 2, 4, 6, 8, 12, and 24 hours. The 24-hour post-dose sample will be collected prior to dosing themselves with aldafermin/matched placebo on Day 2. Additional samples will be collected for C4 testing at the same timepoints as the PK blood sample collections. The window for sample collection for the pre-dose through 8-hour time points is ± 5 minutes. The window for sample collection for the 12- through 24-hour time points is ± 30 minutes.

9.2.4 Week 2 Procedures

Subjects will report to clinic fasted and not dosed with aldafermin/matched placebo. The following procedures will be performed:

Pre-dose:

- Measure vital signs (including temperature, respiratory rate, and seated blood pressure and pulse)
- Record concomitant medications
- Record AEs
- Obtain blood for 10-hour fasted clinical laboratory samples
 - Chemistry
 - CBC
 - INR
 - Lipid panel
 - Lipoprotein particles
 - Lipase
 - C4 and serum bile acids
 - PK (pre-dose)
 - ADAs
 - NAbs

Results for ALT, AST, Total Cholesterol, LDL, HDL, and triglycerides are blinded to the site and sponsor.

In-clinic dosing and dispensing:

- Collect old aldafermin/matched placebo study-drug kit/diary and conduct reconciliation
- Dispense new aldafermin/matched placebo study-drug kit/diary
- Dispense rosuvastatin medication/diary
- Oversee subject's aldafermin/matched placebo study-drug self-administration (from new kit).
- Perform LISSA evaluation

Before clinic discharge:

- Remind subject to bring study-drug kit/diary and to not self-inject aldafermin/matched placebo on clinic visit days
- Schedule Week 4 visit

Lipid-Lowering Therapy Assessment:

The third-party Medical Monitor will evaluate LDL-C results to assess the need for lipid-lowering therapy (refer to [Section 9.4.14](#)).

9.2.5 Week 4 Procedures

Subjects will report to clinic fasted and not dosed with aldafermin/matched placebo. The following procedures will be performed:

Pre-dose:

- [REDACTED]
- Measure vital signs (including temperature, respiratory rate, and seated blood pressure and pulse)
- Record concomitant medications
- Record AEs
- Obtain blood for 10-hour fasted clinical laboratory samples:
 - Chemistry
 - CBC
 - INR
 - Lipid panel
 - Lipoprotein particles

- Lipase
- C4 and serum bile acids
- PK (pre-dose)
- ADAs
- NAbs
- [REDACTED]
- [REDACTED]
- [REDACTED]

Results for ALT, AST, Total Cholesterol, LDL, HDL, and triglycerides are blinded to the site and sponsor.

- Obtain urine for 10-hour fasted laboratory sample collection for:
 - Pre-dose urine pregnancy in all females of childbearing potential

In-clinic dosing and dispensing:

- Collect old aldafermin/matched placebo study-drug kit/diary and conduct reconciliation
- Dispense new aldafermin/matched placebo study-drug kit/diary
- Dispense rosuvastatin medication/diary
- Oversee subject's aldafermin/matched placebo study-drug self-administration (from new kit)
- Perform LISSA evaluation

Before clinic discharge:

- Remind subject to bring study-drug kit/diary and to not self-inject aldafermin/matched placebo on clinic visit days
- Schedule Week 8 visit

Lipid-Lowering Therapy Assessment:

The third-party Medical Monitor will evaluate LDL-C results to assess the need for lipid-lowering therapy (refer to [Section 9.4.14](#)).

9.2.6 Week 8 Procedures

Subjects will report to clinic fasted and not dosed with aldafermin/matched placebo. The following procedures will be performed:

Pre-dose:

- [REDACTED]

- Measure vital signs (including temperature, respiratory rate, and seated blood pressure and pulse)
- Record concomitant medications
- Record AEs
- Obtain blood for 10-hour fasted clinical laboratory samples:
 - Chemistry
 - CBC
 - INR
 - Lipid panel
 - Lipoprotein particles
 - Lipase
 - C4 and serum bile acids
 - PK (pre-dose)
 - ADAs
 - NAbs

■ [REDACTED]
■ [REDACTED]
■ [REDACTED]

Results for ALT, AST, Total Cholesterol, LDL, HDL, and triglycerides are blinded to the site and sponsor.

In-clinic dosing and dispensing:

- Collect old aldafermin/matched placebo study-drug kit/diary and conduct reconciliation.
- Dispense new aldafermin/matched placebo study-drug kit/diary
- Dispense rosuvastatin medication/diary
- Oversee subject's aldafermin/matched placebo study-drug self-administration (from new kit)
- Perform LISSA evaluation

Before clinic discharge:

- Remind subject to bring study-drug kit/diary and to not self-inject aldafermin/matched placebo on clinic visit days
- Schedule Week 12 visit

Lipid-Lowering Therapy Assessment:

The third-party Medical Monitor will evaluate LDL-C results to assess the need for lipid-lowering therapy (refer to [Section 9.4.14](#)).

9.2.7 Week 12 Procedures

Subjects will report clinic fasted and not dosed with aldafermin/matched placebo. The following procedures will be performed:

Pre-dose:

- Measure body weight, BMI, and waist circumference
- [REDACTED]
- Obtain 12-lead ECG (after subject has been supine for at least 5 minutes)
- Measure vital signs (including temperature, respiratory rate, and seated blood pressure and pulse)
- Obtain an MRI-PDFF assessment
- Record prior and concomitant medications
- Record AEs (starting from the when the subject signs informed consent)
- Obtain blood for 10-hour fasted laboratory sample collection for:
 - Chemistry
 - CBC
 - HbA1c
 - Insulin level
 - HOMA-IR calculation
 - [REDACTED]
 - INR
 - Lipid panel
 - Lipoprotein particles
 - Lipase
 - C4 and serum bile acids
 - PK (pre-dose)
 - ADAs
 - NAbs

- ELF panel
- Pro-C3

- [REDACTED]
- [REDACTED]
- [REDACTED]

Results for ALT, AST, Total Cholesterol, LDL, HDL, and triglycerides are blinded to the site and sponsor.

- Obtain urine for 10-hour fasted laboratory sample collection for:
 - Pre-dose urine pregnancy in all females of childbearing potential
 - Urinalysis
 - Urine drug screen

In-clinic dosing and dispensing:

- Collect old aldafermin/matched placebo study-drug kit/diary and conduct reconciliation
- Dispense new aldafermin/matched placebo study-drug kit/diary
- Dispense rosuvastatin medication/diary
- Oversee subject's aldafermin/matched placebo study-drug self-administration (from new kit)
- Perform LISSA evaluation

Before clinic discharge:

- Remind subject to bring study-drug kit/diary and to not self-inject aldafermin/matched placebo on clinic visit days
- Schedule Week 18 visit

Lipid-Lowering Therapy Assessment:

The third-party Medical Monitor will evaluate LDL-C results to assess the need for lipid-lowering therapy (refer to [Section 9.4.14](#)).

9.2.8 Week 18 Procedures

Subjects will report to clinic fasted and not dosed with aldafermin/matched placebo. The following procedures will be performed:

Pre-dose:

- [REDACTED]
- Measure vital signs (including temperature, respiratory rate, and seated blood pressure and pulse)
- Record concomitant medications
- Record AEs
- Obtain blood for 10-hour fasted laboratory sample collection for:
 - Chemistry
 - CBC
 - INR
 - Lipid panel
 - Lipoproteins
 - Lipase
 - C4 and serum bile acids
 - PK (pre-dose)
 - ADAs
 - NAbs

[REDACTED]
[REDACTED]
[REDACTED]

Results for ALT, AST, Total Cholesterol, LDL, HDL, and triglycerides are blinded to the site and sponsor.

In-clinic dosing and dispensing:

- Collect old aldafermin/matched placebo study-drug kit/diary and conduct reconciliation
- Collect old rosuvastatin medication bottle/diary and conduct reconciliation
- Dispense new aldafermin/matched placebo study-drug kit/diary

- Dispense new rosuvastatin medication/diary
- Oversee subject's aldafermin/matched placebo study-drug self-administration (from new kit)
- Perform LISSA evaluation

Before clinic discharge:

- If subject is taking statins, evaluate tolerability and continue therapy to Week 24 for statin naïve or Week 30 for statin experienced
- Record new and/or changes to AEs after aldafermin/matched placebo dosing
- Remind subject to bring study-drug kit/diary and to not self-inject aldafermin/matched placebo on clinic visit days
- Schedule Week 24 (End of Treatment) visit

Lipid-Lowering Therapy Assessment:

The third-party Medical Monitor will evaluate LDL-C results to assess the need for lipid-lowering therapy (refer to [Section 9.4.14](#)).

9.2.9 Week 24 / Early Withdrawal (End of Treatment) Procedures

Subjects will report to this visit fasted and not dosed with aldafermin/matched placebo.

The following procedures will be performed at the Week 24/Early Withdrawal visit:

Pre-dose:

- Measure body weight, BMI, and waist circumference
- [REDACTED]
- Obtain 12-lead ECG (after subject has been supine for at least 5 minutes)
- Measure vital signs (including temperature, respiratory rate, and seated blood pressure and pulse)
- Obtain an MRI-PDFF assessment.
- Undergo a liver biopsy procedure to obtain new tissue
- Record concomitant medications
- Record AEs
- Obtain 10-hour fasted clinical laboratory samples for the following:
 - Chemistry
 - CBC
 - HbA1c
 - Insulin level
 - HOMA-IR calculation

- [REDACTED]
- INR
- Lipid panel
- Lipoprotein particles
- Lipase
- C4 and serum bile acids
- PK (pre-dose) collect for all subjects other than those participating in the Optional PK sub-study
- ADAs
- NAbs
- ELF panel
- Pro-C3

[REDACTED]
[REDACTED]
[REDACTED]

Results for ALT, AST, Total Cholesterol, LDL, HDL, and triglycerides are blinded to the site and sponsor.

Obtain 10-hour fasted clinical laboratory samples for the following:

- Urine pregnancy test (all female subjects of childbearing potential)
- Urinalysis
- Urine drug screen

In-clinic dosing:

- Collect old aldafermin/matched placebo study-drug kit/diary and conduct reconciliation
- Collect old rosuvastatin bottle and conduct reconciliation
- Dispense new rosuvastatin study-drug/diary (only for subjects who were statin experienced at Baseline)
- Oversee subject's aldafermin/matched placebo study-drug self-administration (from old kit) (not applicable for Early Withdrawal subjects)
- Perform LISSA evaluation

Before clinic discharge:

(NOTE: PK sampling before-clinic-discharge is not applicable for Early Withdrawal subjects; however, Early Withdrawal subjects should be scheduled for a 6-week Follow-up visit.)

- Obtain 2-hour post-dose PK blood sample
- Schedule subject for Week 25 Post-Treatment Response Visit

Lipid-Lowering Therapy Assessment:

- The third-party Medical Monitor will evaluate LDL-C results to assess the need for lipid-lowering therapy (refer to [Section 9.4.14](#)).

For Optional PK Sub-study Subjects:

For those subjects participating in the optional PK sub-study, PK samples will be collected pre-dose before subjects dose themselves in the clinic and post-dose at 0.5, 1, 2, 4, 6, 8, 12, and 24 hours. The 24-hour post-dose sample will be collected prior to dosing themselves with aldafermin/matched placebo on Day 2. Additional samples will be collected for C4 testing at the same timepoints as the PK blood sample collections. The window for sample collection for the pre-dose through 8-hour time points is ± 5 minutes. The window for sample collection for the 12- through 24-hour time points is ± 30 minutes.

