8.4 Discontinuation of Subjects from Study Participation

Subjects will be informed that they are free to withdraw from the study at any time and for any reason. The Principal Investigator (PI) may remove a subject from the study if, in the PI's opinion, it is not in the best interest of the subject to continue the study. Subjects may be discontinued due to a change in compliance with an inclusion/exclusion criterion that is clinically relevant and affects subject safety, occurrence of AEs, occurrence of pregnancy, or administration of non-permitted concomitant medication that might affect subject safety or study assessments/objectives. Notification of discontinuation will be made immediately to the Sponsor Medical Monitor or designee. In case of premature discontinuation of study participation, efforts will be made to perform all final EOT and EOS visits/assessments. The date the subject is withdrawn from the study and the reason for discontinuation will be recorded on the subject's Case Report Form (CRF). All withdrawn subjects will be followed

until resolution of any AEs or until any unresolved AEs are judged by the PI to have stabilized.

9 Study Methods

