^c During screening, sites will complete; i) AUDIT-C alcohol consumption questionnaire and, ii) document subject- reported alcohol consumption to confirm whether amounts are within protocol defined limits (refer to exclusion criterion #19)

^d Screening Day -28 MRI-PDFF (includes [REDACTED]) will serve as baseline for efficacy endpoint analysis. The Screening MRI result is valid for up to 8 weeks and may be used for a subject who is re-screened within that time frame. [REDACTED]

^e All subjects are required to have a liver biopsy result at Screening and additional liver biopsy at Week 24. A Screening liver biopsy will be performed only in subjects who do not have a historical biopsy available within 6 months of Screening.

^f Adverse events will be monitored and recorded from subject signing informed consent through follow-up.

^g Serum chemistry will include ALT, AST, ALP, bicarbonate, bilirubin (direct and total), BUN, calcium, chloride, creatinine, CK, GGT, glucose, HDL, LDL, lipase, phosphate, potassium, proteins (albumin, total protein), sodium, total cholesterol, and TG. Lab results for ALT, AST, total cholesterol, LDL, HDL, and triglycerides are blinded to the site and sponsor from Week 2 onward.

^h Creatine Kinase will be collected at Day -42, Day 1 and Week 12, and Week 24.

ⁱ A serum pregnancy test will be performed on all female subjects of childbearing potential at Day -42, -28 Screening visits and Day 1 (pre-dose). A urine pregnancy test will be performed on all female subjects of childbearing potential at Weeks 4, 12, 24, and 30. If the urine pregnancy test is positive, a serum pregnancy test will be performed to confirm

results.

^j Urine drug and alcohol screens may be repeated during treatment for subjects suspected of excessive alcohol intake or to rule out association with a safety event

^k C4 and bile acid testing will be collected at Day 1 and Weeks 2, 4, 8, 12, 18, 24, 25 and 30. In addition, for subjects participating in the optional PK sub-study, additional C4 will be tested at the same timepoints as the PK blood sample collections: Day 1 and Week 24 at pre-dose, and post-dose at 0.5, 1, 2, 4, 6, 8, 12, and 24 hours.

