9.4.2 Liver Biopsy

Subjects who meet the Screening criteria of an available liver biopsy tissue specimen within 6 months of Screening will not be required to undergo a new liver biopsy. For subjects who have participated in a prior study involving an investigational agent for NASH, the prior liver biopsy obtained within 6 months may be used only if the subject was treated with placebo. All other subjects will be required to undergo a liver biopsy per the study site's local standard-of-care procedure during the Screening period and prior to randomization. Sites should not perform a local reporting of the NAS or fibrosis score at either Screening or

Week 24 to the site in order to maintain the blinding of the primary endpoint. Tissue from all subjects will be collected, prepped and sent to the Central Study Pathologist for review for the absence/presence of NASH as defined in the Biopsy Manual. Liver biopsies with histologically confirmed NASH will be further assessed using the NAS established and validated by the NASH CRN (see [Appendix 1](#)). Liver biopsies will be assessed for degree of steatosis (0 – 3), lobular inflammation (0 – 3), hepatocellular ballooning (0 – 2), and fibrosis (0 – 4). The first three components will be added together to determine the NAS that ranges from 0 to 8. Liver biopsies with an NAS of <4 will be considered exclusionary. Subjects with liver biopsies with Stage 4 fibrosis, consistent with cirrhosis, will be excluded from this study. The Week 24 biopsy should be obtained \leq 7 days before last dose of aldafermin/matched placebo.

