9.4.3 Magnetic Resonance Imaging (MRI)

All enrolled subjects will have a Baseline (from the Screening result) and EOT MRI of the liver to evaluate [REDACTED] liver fat. Subjects will have an MRI performed at Screening Day -28 and at Weeks 12, 24 (EOT), and 30 (EOS). MRI-PDFF will be reported on all MRI imaging scans. Scans should be performed at high field strength (3T preferred, 1.5T acceptable), without the administration of oral or intravenous contrast material. MRI examinations will include a six-echo gradient recalled [REDACTED]
[REDACTED]

The initial study MRI examination will be performed during the Screening period prior to randomization. An MRI-PDFF value of $\geq 8\%$ at Screening as assessed by the central radiology core is one of the inclusion criteria for the study. Therefore, for subjects who require a liver biopsy as part of the trial (for whom no recent liver biopsy is available), it is recommended that the liver biopsy be scheduled no sooner than 7 business days after (electronic) transmission of the screening MRI examination to the central radiology core to allow adequate time for processing and reporting of the result. The screening MRI-PDFF results will be reported to the individual site no more than 5 business days after the MRI examination is received. The Screening MRI result is valid for up to 8 weeks and may be used for a subject who is re-screened within that time frame. None of the on treatment or post treatment MRI results (other than incidental findings) will be provided to the sites. Week 24/EW/EOT MRI-PDFF should be performed before the last dose of aldafermin/matched placebo.

For both Screening and EOT/Early Withdrawal MRI examinations, subjects should consume nothing by mouth (NPO) for 4 hours prior to their MRI appointment. Medications and small amounts of water are acceptable.

Prior to MRI, all subjects should undergo safety assessment per institutional protocols and per the guidelines of the local Institutional Review Board. Subjects should be questioned regarding claustrophobia, pregnancy or potential pregnancy, size or weight exceeding the capabilities of the MRI system, metal implants, and other potential safety issues.

Detailed instructions for MRI procedures and provision of examination to a central reader will be presented in a separate MRI Manual.

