Subjects whose LDL-C values are still not adequately managed, (defined as > 100 mg/dL and > 15 mg/dL above their Day 1 LDL-C value) and are currently receiving their maximum tolerated rosuvastatin dose plus ezetimibe, will be discontinued from the study and an early withdrawal study visit completed. The follow up/EOS visit should be scheduled for 6 weeks after the early withdrawal study visit. Refer to [Appendix 4](#), Rosuvastatin Dose Reduction Algorithm and [Appendix 5](#), Adverse Event of Statin-Related Muscle Pain or Creatine Kinase (CK) Algorithm.

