12.5 Efficacy Analyses

12.5.1 Primary Efficacy Analysis

The primary efficacy endpoint for this study is the histologic response at Week 24, defined as a subject achieving an improvement in liver fibrosis greater than or equal to one stage (NASH CRN fibrosis score) with no worsening of steatohepatitis (defined as no increase in NAS for ballooning, inflammation, or steatosis) after 24 weeks of treatment.

Subjects with two biopsies (baseline and post-baseline) will be considered for this analysis only if the second biopsy is taken after at least 12 weeks (i.e., 50% of the intended 24-week treatment period) of treatment on study drug. For the primary efficacy analysis, missing histologic responses at Week 24 will be imputed using a multiple imputation (MI) method under the assumption of missing at random. The details of the MI method will be provided in the SAP.

The primary efficacy endpoint will be analyzed using the MCP-Mod (Multiple Comparison Procedure – Modelling) approach to assess the dose-response relationship. Within the framework of the MCP-Mod procedure, the null hypothesis of no dose-response will be tested at the 5% significance level against the alternative hypothesis that there is a dose-response. The details of the MCP-Mod approach will be provided in the SAP.

Sensitivity analyses will include imputations with missing histologic responses as both responders and non-responders, and analysis with the assumption of missing not at random (e.g., pattern mixture models).

The primary efficacy analyses will be performed using the ITT population. The Full-Analysis and PP populations will be used as sensitivity analyses.

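### The early-withdrawal visit list includes a liver biopsy with no minimum time on treatment, so a subject leaving before Week 12 could have one that the primary analysis does not consider

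*Protocol*

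**What the plan says.** Protocol 9.2.9 gives a single list of procedures for the Week 24/Early Withdrawal visit. One item is "Undergo a liver biopsy procedure to obtain new tissue". It has no condition on time on treatment. The same list marks in-clinic self-injection as "not applicable for Early Withdrawal subjects" and exempts early leavers from PK sampling before discharge, but says nothing similar about the biopsy. Table 4 places the post-baseline biopsy in a combined Week 24/EW column.

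The biopsy-specific text is narrower. Table 4 footnote e reads "All subjects are required to have a liver biopsy result at Screening and additional liver biopsy at Week 24". Section 9.4.2 begins its timing rule with "The Week 24 biopsy should be obtained" and ties that biopsy to the 7 days before the last dose. Neither mentions early withdrawal. The MRI section (9.4.3) does: "24/EW/EOT MRI-PDFF should be performed before the last dose".

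Section 8.4 says that after premature discontinuation "efforts will be made to perform all final EOT and EOS visits/assessments". Section 9.4.14 says that subjects whose LDL-C stays uncontrolled on maximum tolerated rosuvastatin plus ezetimibe "will be discontinued from the study and an early withdrawal study visit completed". It names no earliest week.

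For the primary analysis, Protocol 12.5.1 considers a subject with two biopsies "only if the second biopsy is taken after at least 12 weeks" of treatment on study drug. Missing Week 24 responses are multiply imputed.

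**The concern.** The visit schedule and the analysis rule use different thresholds. The schedule sets none, whereas the primary analysis sets 12 weeks. A subject who leaves at Week 6, for example, is on the visit list for a liver biopsy whose result the protocol-defined primary analysis sets aside. A liver biopsy is the most invasive item on that list, and the protocol gives no stated purpose for one taken this early.

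A smaller data question follows. SAP 2.3 uses nominal visits and defines no analysis windows. If an early biopsy is recorded under the shared visit label, it might enter secondary summaries as a Week 24 result.

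**Working it through.** **Step 1. Is the biopsy expected of an early leaver?**
- In favour: 9.2.9 puts it in the shared list and qualifies other items there, but not this one. Table 4 has the combined column. Section 8.4 seeks all end-of-treatment assessments.
- Against: footnote e and 9.4.2 name Week 24 only. Section 9.4.3 shows that early withdrawal was named where it was meant. Section 8.4 asks for efforts only.
- Result: unclear. A site could reasonably follow the visit list.

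**Step 2. Can an early-withdrawal visit fall before Week 12?**
Yes. Section 8.4 allows withdrawal at any time. Section 8.3 stops study drug for specified adverse events and for CK or liver signals, with no earliest week. The LDL-C route in 9.4.14 also has no earliest week. That route is likely to be slow, because rosuvastatin starts at Week 2 and ezetimibe comes second. The dosing algorithm (Appendix 3) is not visible, so its timing cannot be checked.

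**Step 3. What would use the result?**
- Primary analysis: not considered (12.5.1). The visible imputation model (SAP 5.1.5) uses only treatment group and baseline fibrosis stage, so on that text the early biopsy would not inform the subject's imputed response either.
- Secondary histology (SAP 5.2: NASH resolution, combined response, fibrosis and NAS change): no visible 12-week condition.
- Full Analysis and Per Protocol sets (SAP 2.1): no visible minimum treatment time. The Per Protocol set may exclude intercurrent events that affect the biopsy.
- Listings: possible.

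**Step 4. Stated power.**
SAP 1.3 bases power on 32 per group, after 15% dropout from 38 (38 × 0.85 = 32.3). As a check, a max-contrast test was simulated at the two-sided 5% critical value with pooled binomial variance and 40,000 runs per scenario. The candidate models are not visible, so the contrasts were built on the logit scale from the six stated scenarios (an assumption).

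| | Power over the six scenarios (%) |
|---|---|
| SAP Table 1 | 92, 90, 93, 85, 87, 90 |
| Simulated, 32 per group | 93.2, 91.3, 93.3, 86.0, 88.8, 90.5 |
| Simulated, 38 per group | 96.4, 95.2, 96.8, 91.6, 93.4, 95.1 |

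The SAP figures agree within 2 points with 32 per group and lie about 4 to 7 points below the results for 38. The stated power therefore already leaves out all assumed dropouts. Dropping biopsies taken before Week 12 does not change it.

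**Step 5. How many subjects?**
- Ceiling: 152 × 0.15 = 22.8, about 23. By the SAP's count, 152 − 4 × 32 = 24. This requires every dropout to leave before Week 12 and be biopsied.
- Floor: 0.
- Illustration: 22.8 × (share leaving before Week 12) × (share of those biopsied). The documents give neither share; both are assumed.

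| Share leaving before Week 12 | Share biopsied | Subjects |
|---|---|---|
| 0.25 | 0.25 | 1.4 |
| 0.50 | 0.50 | 5.7 (5.7/152 = 3.8%) |
| 0.75 | 0.75 | 12.8 |

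**The case against.** The best reply is that nothing here conflicts. Section 12.5.1 is a rule for one analysis. It allows for second biopsies taken early and says how that analysis treats them. Collecting a sample and leaving it out of one analysis is not inconsistent. Early histology may also have other uses: the secondary endpoints and the Full Analysis set carry no visible 12-week condition, and the planned missing-not-at-random sensitivity analyses might draw on it. The SAP overrides the protocol where they differ, and the bodies of SAP 5.1.2 (estimand), 5.1.6 (sensitivity analyses) and 10 (deviations from the protocol) are not visible. The Biopsy Manual is not available either.

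Much of this stands, and it rules out several stronger readings that a reader might infer:
- That the protocol mandates the early biopsy. Footnote e, 9.4.2 and the wording of 8.4 do not support that.
- That the tissue would have no use. The visible text leaves secondary, sensitivity and listing uses open.
- That the SAP has dropped the 12-week rule. Its visible text does not repeat the rule, but the sections where it would belong cannot be read.
- That power or the primary analysis is harmed. Neither is.

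What remains is that no visible text tells a site whether to biopsy a subject who leaves before Week 12, or why.

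**Conclusion.** The point holds as an ambiguity with a patient-safety side, and it is an optional improvement. The visit list and the 12-week rule are not reconciled in any visible text, so some early leavers could have an invasive procedure that the protocol-defined primary analysis does not consider. The size is unknown. About 23 of 152 is a ceiling under the planned 15% dropout, and the likely number is far smaller. The illustrative counts of about 1 to 13 rest entirely on assumed shares. Confidence is medium, because the conclusion depends on the hidden SAP sections not giving early biopsies a defined role.

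**What to change.** In Protocol 9.2.9, Section 9.4.2 and Table 4 footnote e, add one phrase: the early-withdrawal biopsy is done only in subjects who have had at least 12 weeks of study treatment, unless it is clinically indicated. The exception keeps the option open for, say, a liver safety signal.

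First check SAP 5.1.2 and 5.1.6. If either uses biopsies taken before 12 weeks, keep the procedure and state its purpose in 9.4.2.

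The cost is the wording change plus the loss of a few early biopsies from exploratory secondary and sensitivity histology analyses. The protocol-defined primary analysis, the sample size and the stated power stay as they are.
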